7.1.2 Secondary study outcomes

1. Comparison of the quantitative primary and secondary results of MagnetOsTM Granules to the results of AttraX® Putty from the AxA study (unpaired);
2. Relation between successful posterolateral fusion and interbody fusion at one-year follow-up (assessed on CT-scans);
3. Posterolateral spinal fusion rate at two years follow-up compared to the fusion rate at one-year follow-up (assessed on CT-scans);
4. Effect of blinding on perceived donor site pain;
5. Incidence of long-term complications and relation with risk factors in the combined population of this study and the AxA study.

7.1.3 Other study outcomes

This study provides the opportunity to further investigate several outcomes in a cohort of 100 spondylodesis patients, not related to the comparison of MagnetOsTM Granules and autograft.

1. Changes in EQ-5D-5L, ODI and VAS pain scores over time;
2. Relation between clinical outcomes and fusion status at one-year follow-up;
3. Satisfaction with treatment;
4. Effect of nicotine use on fusion;
5. Effect of NSAID use on fusion.

7.2 Randomization, blinding and treatment allocation

Randomization for the allocation of the graft type will be performed with use of a computerized random-number algorithm. The randomization scheme will be maintained at the UMC Utrecht by the central principal investigator and study coordinator. The orthopaedic surgeon will be blinded to the allocation side of MagnetOsTM Granules, and thereby the contralateral allocation of autograft, as long as possible. He/she will receive an envelope containing the randomization of the patient which should be opened during surgery just

before the graft is needed (see suggested surgical technique, Appendix B). The iliac bone graft has to be taken from the same side where the autograft will be applied for posterolateral fusion according to the randomization. This will not be communicated to the patient. Whenever possible, bone harvesting will be done without making an additional skin incision.

In case an intra-operative decision is made to perform something different than what was intended for study enrollment, like for example to use local bone graft only or an uninstrumented spinal fusion, the patient will be considered a per-operative withdrawal and will not be treated with MagnetOs™ Granules. These patients will be replaced as described in paragraph 7.5.

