2.2 Secondary objectives

1. To compare the quantitative primary and secondary results of MagnetOsTM Granules to the results of Attrax® Putty from the AxA study (unpaired);
2. To investigate the relation between successful posterolateral fusion and interbody fusion, assessed at the one-year CT-scans used for the primary objective;
3. To compare the posterolateral spinal fusion rate of both MagnetOsTM Granules and autograft at one year with the fusion rates after two years, by using CT-scans;
4. To investigate the effect of blinding on perceived donor site pain, based on outcome measures reported by patients unblinded to the iliac crest donor site in comparison to these outcomes of the blinded patients from the AxA study;
5. To combine the study populations of the current study and the AxA study to investigate a) adjacent segment disease, in relation to length of construct and sagittal balance and b) risk factors for failures.

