Although iliac crest donor site morbidity is often reported by patients, the relevance of donor site pain is disputable when the bone is harvested via the same incision as used for the spinal fusion.³ The preliminary results of the AxA study indeed indicate that there is no relation between the real donor site and the iliac crest that is indicated by blinded patients. To determine if the often reported high incidence of donor site pain can be explained by the knowledge of the patient where the bone graft was taken, we will not blind the patients for the donor site in this study. The outcomes measures reported by patients unblinded to the iliac crest donor site will be compared to the outcomes of the blinded patients from the AxA study.

5. Combine the study populations of the current study and the AxA study

To combine the study data of both the current study and the AxA study will allow investigations on more infrequent phenomena on a relatively large population. Such a phenomenon is for example adjacent segment disease. This is a longterm complication where the adjacent joints and intervertebral disc may wear faster and cause degenerative disease. The occurrence of adjacent segment disease may be related to length of the construct and restoration of the sagittal balance. The occurrence of typical complications like infection and pseudoarthrosis can be related to risk factors like comorbidities, smoking, length of instrumented segment and so on.

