9.3 Analysis of secondary outcomes

1. To compare the quantitative primary and secondary results of MagnetOs™ Granules to Attrax® Putty a McNemar's test will be used as well as the mentioned GEE model;
2. As mentioned for the primary analysis, the odds-ratios and 95% confidence intervals for fusion rates of MagnetOs™ Granules and autograft will be calculated by using the GEE model. This model also allows to assess the effect of an additional interbody fusion;
3. For the comparison of the fusion rate after two years, the same method as for the primary efficacy analysis will be used;
4. VAS pain scores will be analyzed using the paired t-test, or Wilcoxon signed rank test in case of not-normally distributed data. To investigate the effect of blinding on perceived donor site pain, pain scores reported by the patients of this study and the AxA study will be compared using the unpaired t-test or Mann-Whitney U test.
5. To investigate risk factors of both study populations regression analysis will be done.

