After instrumentation and preparation of the fusion trajectory the envelope containing the allocation side of the autograft and MagnetOs condition and thereby the allocation of the iliac harvesting side, is opened.

Step 8: Harvesting of iliac crest autograft

Only one side of the pelvis can be used for iliac crest bone harvesting. This must be the same side as allocated to the autograft posterolateral spine fusion condition. The surgeon can use any technique that exposes the iliac crest to obtain corticocancellous bone, but preferably no additional skin incision is made and harvesting through a posterior cortical window is advised. A total autograft volume of 8-10cc per side and fusion level is intended. The contribution of iliac bone graft to this volume has to be at least 50%. For example in a L3-S1 three-level fusion with 10cc of local bone, another 20cc of bone from the iliac crest is required to reach 3x10cc. If local bone is 20cc, 5cc of this will not be used as local bone can only be 15cc (= 50% of 30cc). If the 10cc per level and side cannot be reached because of limited iliac bone graft, the autograft volume has to be extended with local bone. In case the volume remains below 8cc per side, this is accepted as a consequence of autologous bone grafting. The MagnetOs condition will always be 8-10cc and not combined with local bone.

Step 9: Placement of the graft

Both grafts, the autograft and MagnetOsTM granules, are placed on the allocated side around the instrumentation and in the decorticated lateral gutters, bridging the dorsal surfaces of the transverse processes, facets and laminae. No graft is placed on the dura. No additional substances like blood or bone marrow are added. If not yet done at step 3, the rod fixation is inserted at this time.

Step 10: Patient closing

The patient is closed using the technique preferred by the surgeon. If vancomycin or another antiseptic procedure is used, this should be recorded on the surgical form of the CRF.

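### Section 7.2 withholds the bone-harvest side from patients, whereas secondary objective 4 needs patients who know it

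*Combined protocol and SAP*

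**What the plan says.** Section 7.2, which governs randomization and blinding, ties the iliac harvest to the side randomized to autograft. The next sentence reads: "This will not be communicated to the patient". Appendix B, step 8, repeats the link between the two sides: "This must be the same side as allocated to the autograft posterolateral spine fusion condition".

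The objectives point the other way. Section 2.2 item 4 relies on "outcome measures reported by patients unblinded to the iliac crest donor site" and compares them with the blinded patients of the AxA study. Section 2.3 item 4 gives the reason. The team wants to know whether the high reported incidence of donor site pain "can be explained by the knowledge of the patient where the bone graft was taken", and therefore states: "we will not blind the patients for the donor site in this study".

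Section 7.1.2 item 4 makes this a named outcome, "Effect of blinding on perceived donor site pain". Section 9.3 item 4 gives the analysis: "pain scores reported by the patients of this study and the AxA study will be compared using the unpaired t-test", with the Mann-Whitney test as the alternative.

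**The concern.** The exposure in secondary objective 4 is what the patient knows. AxA supplies the patients who did not know the harvest side, and this trial is meant to supply those who do. The only operational instruction on the matter tells staff to keep the side from the patient, and no section tells them to disclose it.

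A site that follows section 7.2 to the letter therefore produces patients in much the same state as the AxA patients. The comparison would still run and would still yield a p-value, but it would not address its question. The likeliest harm is a finding of no difference reported as evidence that knowing the donor site does not influence pain, when the two groups may not have differed in that knowledge.

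**Working it through.** The plan gives no effect size, standard deviation or power for this objective, so there is no figure to reproduce. The requirement of 84 evaluable patients in section 4.4 belongs to the CT endpoint and does not enter here. The check is a comparison of the texts.

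1. **What must the patient know?** Sections 2.2 and 2.3, item 4 of each: the side from which iliac bone was taken. Patients here are unblinded to it, and AxA patients were blinded.

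2. **What does section 7.2 withhold?** The sentence before the instruction says that iliac bone comes from the side that receives autograft. *This* most naturally refers to that harvest side.

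3. **Can a narrower reading reconcile them?** Suppose *This* meant only the graft allocation, so that a patient could be told the harvest side but not the graft side. The protocol does not say so. Section 7.2 and Appendix B, step 8, make the two sides the same, so telling one discloses the other. Chapter 3 allows a different harvest side after previous harvesting or for anatomical reasons, which separates the two in some patients only. Even on this reading, no section instructs staff to disclose the harvest side.

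4. **Would patients find out unaided?** Chapter 3, section 7.2 and Appendix B all prefer harvesting through the spinal incision, so often no separate scar would show the side. Section 2.3 reports from the preliminary AxA data that there was "no relation between the real donor site and the iliac crest that is indicated by blinded patients". Patients who are not told may well not know.

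5. **What does the planned comparison then estimate?** Let δ be the true mean difference in pain score between patients who know the side and patients who do not, and let q be the share of this trial's patients who do not know. Assume that those patients report pain as blinded AxA patients do, and that the studies are otherwise alike. The expected difference between the studies is then

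 D = (1 − q) × δ + q × 0 = (1 − q) × δ.

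 Neither q nor δ is in the documents, so only the range can be shown:
 - q = 0 (all know, as section 2.3 intends): D = δ
 - q = 0.25: D = 0.75 δ
 - q = 0.50: D = 0.50 δ
 - q = 1 (section 7.2 followed and nobody learns the side): D = 0, whatever δ is

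6. **What else depends on patient knowledge?** The CT panel works blinded on de-identified scans (section 7.4.2, Appendix C). The primary test is within-patient on CT fusion. Neither depends on what the patient is told.

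**The case against.** The best reply is that the intent is not in doubt. Two sections say that patients are unblinded, one of them with a reason, and an outcome and an analysis follow from it. The design is described as observer blinded, and no design statement calls patients blinded. The sentence in section 7.2 may be a remnant of the AxA protocol; Appendix A still names AttraX Putty in its sample size paragraph, which shows that text was carried over. That origin is an inference, but a plausible one. The loss also occurs only if sites act on section 7.2, and the objective is a non-randomized comparison between two studies with no stated power, so its evidence is modest in any case.

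Most of this stands, and it bears on how serious the point is. It does not remove the contradiction: sites work from the procedural section, and that section says the opposite of the objective.

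A reader might also infer that the trial cannot show which patients knew the side. The items listed in sections 7.3.1 to 7.3.3 include the actual harvest side, pain scores for both iliac crests and a pain drawing, and none asks what the patient knows or believes. The documents do not support the stronger conclusion. The full eCRF and letter E1 are not part of the public text. The AxA result shows that the team had some means of learning which crest a patient indicated, although the means is not stated. Once every patient is told, the exposure is set by protocol, and a record of knowledge becomes a check on delivery; its absence would not be an inconsistency.

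**Conclusion.** The point holds as a contradiction in the text. Section 7.2 as written removes the exposure that sections 2.2, 2.3, 7.1.2 and 9.3 (item 4 in each) depend on. If it is followed and patients do not otherwise learn the side, the section 9.3 comparison cannot estimate an effect of blinding.

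The consequence is limited to secondary objective 4. No effect size or loss of power can be computed from the documents; the range in the working is structural and rests on the assumptions stated there.

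Three stronger readings are not supported:
- That trial blinding or the primary result is compromised. The blinded CT assessment does not depend on what patients know.
- That practice differs between sites. Nothing in the documents suggests it.
- That the number of planned iliac pain scores measures the damage. A count of scores measures neither bias nor precision, and section 9.3 does not say which visits or sides enter the comparison.

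**What to change.** Amend the sentence in section 7.2 to agree with sections 2.2 and 2.3: patients are told the harvest side before the first postoperative pain questionnaire, which Table 7.1 places at 6 weeks. Check that information letter E1 says the same.

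Optionally, if the eCRF does not already capture it, record that the patient was told. Alternatively, ask once which side the patient understands was used, after the iliac pain scales have been completed. Asking before the scales, or at every visit, could draw attention to that side and could add a difference from AxA, whose questionnaire is not described.

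The cost is one sentence, a check of one letter, and an amendment notified to the ethics committee under section 11.3. The option adds one eCRF field or one patient question. Visits, imaging, surgery, CT-panel blinding and the primary analysis stay as they are. The change does not remove other differences between the two studies; it only ensures that the intended contrast in knowledge is part of the design.

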7.3 Study procedures

Figure 7.1 illustrates the timing of the different study procedures that are described below. Procedures that are not part of standard care in one or more participating centers are marked bold.

All study data will be entered in electronic Case Report Forms (eCRFs) using Castor EDC. To limit missing data and ensure timely completion, the patient questionnaires are preferably filled out digitally by using the email function in Castor EDC. If patients prefer paper questionnaires, they should be completed at the outpatient clinic.

De-identified copy of all corresponding images will be send to the principal investigator at the UMC Utrecht.

Table 7.1: Timing of study procedures and data collection. Procedures that are not part of standard care in one or more participating centers are marked bold. Abbreviations: d = days, wks = weeks, mos = months, yr(s) = year(s).

CRF form	Preop	Perop	1-5 d	6 wks (±14d)	3 mos (±21d)	1 yr (+3mos)	2 yrs (±2mos)
	A	B	C	D	E	G	H
Demographics	x						
Baseline data							
Treatment details		x					
Clinical evaluation	x		x	x	x	x	x
X-rays	x		x	x	x	x	x
CT-scan						x	x ¹
Patient questionnaires	x			x	x	x	x

¹ Only applies to patients that scored a doubtful fusion or non-union in any of the relevant levels at the one-year CT scan (see Appendix C)

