7.3.3 Planned follow-up moments

The subsequent follow-up moments will take place at the outpatient clinic and are based on the standard care at the UMC Utrecht. The data described below will be collected at 6 weeks, 3 months, 1 year and 2 years postoperatively. The questionnaires, CT-scan at 2 years follow-up in case of no or doubtful fusion at 1 year follow-up, and depending on the local follow-up protocol the CT-scan at one year follow-up and/or X-ray at two years follow-up, are extra for this study. In addition to the baseline questionnaires, treatment satisfaction will be assessed with a Numeric Rating Scale (NRS).

6 weeks (±14 days; CRF C)

- Complications / (serious) adverse events
- Disease related medication use (including NSAID use)
- Questionnaires
 - EQ-5D-5L
 - ODI
 - NRS satisfaction
- VAS pain score
 - Back pain related to diagnosis
 - Leg pain related to diagnosis
 - Pain in left iliac crest

- Pain in right iliac crest
- Pain drawing
- Imaging
 - Standing anteroposterior and lateral radiographs
- Radiologic evaluation by treating surgeon (indications for failure or deformation / instability)

3 months (\pm 21 days; CRF D)

- Complications / (serious) adverse events
- Disease related medication use (including NSAID use)
- Questionnaires
 - EQ-5D-5L
 - ODI
 - NRS satisfaction
- VAS pain score
 - Back pain related to diagnosis
 - Leg pain related to diagnosis
 - Pain in left iliac crest
 - Pain in right iliac crest
 - Pain drawing
- Imaging
 - Standing anteroposterior and lateral radiographs
- Radiologic evaluation by treating surgeon (indications for failure or deformation / instability)

1 year (12-15 months; CRF F)

- Complications / (serious) adverse events
- Disease related medication use (including NSAID use)
- Questionnaires
 - EQ-5D-5L
 - ODI
 - NRS satisfaction
- VAS pain score
 - Back pain related to diagnosis
 - Leg pain related to diagnosis
 - Pain in left iliac crest

- Pain in right iliac crest
- Pain drawing
- Imaging
 - Standing anteroposterior and lateral radiographs
 - CT-scan
- Radiologic evaluation by treating surgeon (indications for failure or deformation / instability)
- Fusion assessment based on CT-scan by treating surgeon per level and per side in three planes, without the distinction between graft-related or non-graft-related fusion as described in Appendix C.

2 years (22-26 months; CRF G)

- Complications / (serious) adverse events
- Disease related medication use (including NSAID use)
- Questionnaires

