9.4 Other study parameters

The following information will be reported and reviewed, but will not influence the comparisons between the treatment conditions as this is an intra-patient model.

- Demographics
- Nicotine use
- Pre-operative diagnosis
- Medical history
- Concurrent medical issues
- ASA classification
- Disease related medication use
- NSAID use
- Perioperative data
- Length of hospital stay
- EQ-5D-5L
- ODI
- Pain drawing
- NRS satisfaction

The clinical outcome measures, the EQ-5D-5L, ODI and VAS, will be analyzed with repeated measurements to assess changes over time. For continuous data, an independent t-test or Mann Whitney U test (depending on the distribution of the data) will be used to compare the

clinical outcomes of fused and non-fused patients. For categorical data, the Chi-square test will be used. A logistic regression analysis will be performed to analyze the effects of smoking and NSAID use on fusion status.

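### The one-year comparison of clinical outcomes between fused and non-fused patients may partly reflect patients knowing their CT result, because the plan does not say which comes first

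*Combined protocol and SAP*

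**What the plan says.** Section 7.1.3 lists, among the other outcomes, "Relation between clinical outcomes and fusion status at one-year follow-up". Section 9.4 names the measures: "The clinical outcome measures, the EQ-5D-5L, ODI and VAS, will be analyzed with repeated measurements to assess changes over time". It then plans an independent t-test or Mann-Whitney U test for continuous data, and a chi-square test for categorical data, on the "clinical outcomes of fused and non-fused patients". It includes no term or sensitivity analysis for what the patient has been told.

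On data collection, section 7.3 says that "the patient questionnaires are preferably filled out digitally by using the email function in Castor EDC". It adds: "If patients prefer paper questionnaires, they should be completed at the outpatient clinic". Neither route is timed against the CT or the consultation.

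Section 7.3.3 puts the one-year questionnaires, radiographs and CT in the same window of 12-15 months, and Appendix C gives that window for the CT. The one-year data list also includes "Fusion assessment based on CT-scan by treating surgeon per level and per side in three planes". The blinding in section 7.4.2 and Appendix C keeps graft side from the central panel; it does not concern what the patient knows about fusion.

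**The concern.** Pain, disability and health status are self-reported, and a patient who has just heard that the spine has not fused may score them differently from one who has not. If some patients answer after the consultation, the groups in section 9.4 differ in two respects: fusion status, and having heard about it. The planned tests cannot separate the two. Without a recorded disclosure date, an analyst could not separate them afterwards either.

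At stake is the interpretation of one exploratory comparison. The rationale in section 3 says that clinical outcome does not really reflect fusion in the first years. If so, the true difference at one year is small, and even a modest disclosure effect could make up much of whatever difference is seen.

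**Working it through.** **The plan's own figure.** The documents give no sample size, power or effect size for the fused versus non-fused comparison. The figure that can be checked is the 84 patients for the primary comparison (section 4.4, Appendix A).
- Wald formula: n = (1.645 + 0.842)² × 0.30 / 0.15² = 82.4, rounded up to 83.
- Exact enumeration of the score test for paired proportions at n = 84, with discordance 0.30 and true difference 0: power 0.80098, as in the Appendix A table.
- Allowance for 15% not evaluable: 84 / 0.85 = 98.8, so 99, consistent with 100 enrolled.

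The figure reproduces, and nothing below changes it.

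**Order of events.** Setting sections 7.3, 7.3.3, 7.4.2, 9.4 and Appendix C side by side:
- Forms and CT share a window of up to three months.
- The treating surgeon reads the CT for fusion.
- An e-mailed form can be answered on any day in the window; a paper form can be filled in before or after the consultation.
- Section 7.3.3 lists questionnaires above imaging, but that is a list of data items, not a sequence.

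The order is therefore open.

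**Illustration of size.** Inputs from section 4.4: 100 enrolled with 15% not evaluable, so 85; 50% fusion per side; 70% concordance, so 30% discordance. Treating each patient as one left-right pair:
- fused on both sides: 0.50 − 0.30/2 = 0.35, and 0.35 × 85 ≈ 30
- fused on one side only: 0.30 × 85 ≈ 26
- fused on neither side: 1 − 0.35 − 0.30 = 0.35, and 0.35 × 85 ≈ 30

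Section 9.4 does not define a fused patient. Taking it as both sides fused gives 30 versus 55.

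Assumptions not in the documents: VAS SD 25 mm; no true effect of fusion; disclosure worsens the score of a patient given bad news by 2.5 to 10 mm.

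Standard error of the difference: 25 × √(1/30 + 1/55) = 5.67 mm.

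Two-sided 5% false-positive rate for an average shift s (normal approximation): 1 − Φ(1.96 − s/5.67) + Φ(−1.96 − s/5.67).

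*Only patients fused on neither side hear bad news.* They make up 0.35/0.65 = 54% of the non-fused group, so the average shift runs from 2.5 × 0.54 ≈ 1.3 mm to 10 × 0.54 ≈ 5.4 mm.
- s = 1.3: s/SE = 0.23; 0.042 + 0.014 = 5.6%, about 6%
- s = 5.4: s/SE = 0.95; 0.157 + 0.002 = 15.8%, about 16%

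*All 55 patients not fused on both sides are affected.*
- s = 2.5: 7%
- s = 5: 14%
- s = 10: 42%

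If every form is completed before disclosure, this shift is zero and the rate is 5%.

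**The case against.** The strongest reply is that the mechanism is inferred. The documents do not say that patients are told a fusion verdict, when, or in what terms. That stands: the point is that the order is open, and a reader should not infer that the comparison is known to be contaminated.

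Section 2.3, item 4 may tempt a reader to say that the protocol accepts that knowledge changes reported pain. It does not. The study sets out to determine whether "the often reported high incidence of donor site pain can be explained by the knowledge of the patient where the bone graft was taken". That is a question, and it concerns the harvest site, not fusion status.

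The comparison is also exploratory, unadjusted and not randomised, and section 7.1.3 sets it apart from the graft comparison. Confounding, for example by diagnosis or number of levels, would remain whatever the timing of the forms. This stands and limits the priority. It does not remove a source of bias that can be avoided at little cost.

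Two extensions fail:
- **Satisfaction.** It is collected, but section 9.4 does not name it among the clinical outcome measures.
- **Two years.** The extra CT is only for patients with doubtful fusion or non-union, so the recall itself may signal status. But the planned relation is at one year, and an ordering rule at two years could not undo knowledge gained earlier.

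The size is uncertain too. Section 3 calls unilateral fusion sufficient, so patients fused on one side need not hear bad news, which is why the lower range leads. Defining fused as either side would put only the 30 patients fused on neither side in the non-fused group, and the higher rates would return. If the panel's reading defines status, disagreement with the surgeon's reading would dilute the effect without removing it.

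**Conclusion.** The point holds as a limited one. The plan leaves open whether one-year EQ-5D-5L, ODI and VAS are reported before or after the patient hears the surgeon's CT reading, so a difference between fused and non-fused patients could partly reflect that knowledge. The documents do not support the stronger conclusion that the trial will report a false clinical effect of fusion.

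The size is unknown. The range of about 6% to 16% rests on the 30/55 split, an assumed SD of 25 mm, no true effect of fusion, and bad news reaching only patients fused on neither side, all of them before they answer. A smaller share told first would lower it. The 42% figure needs a 10 mm shift averaged over all 55 patients and should not be the headline. This is a worthwhile refinement of an exploratory analysis.

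**What to change.** In section 7.3, require the one-year questionnaires to be completed before the CT result is discussed with the patient: e-mail link sent ahead of the visit, or paper form filled in before the consultation. Record the date of completion and the date the result was given.

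In section 9.4, keep all forms in the main fused versus non-fused comparison, so that late responders are not lost. Add a sensitivity analysis restricted to forms completed before disclosure, and describe the result as an association.

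The cost is slightly tighter visit logistics and one extra date field. The rule cannot guarantee an uninformed patient, because surgeons also read the radiographs for failure and bone bridging (section 7.4.1), but it removes the most direct route.
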